## 6.3. Investigational Device

[figure not shown]
[figure not shown]
- Product Name : Niti-S SPAXUS™ Stent
- Manufacturer : Taewoong Medical Co., Ltd.
- Item Classification : Orthopaedic materials [B03000]  
*As a newly developed medical device, there is no designated subcategory*

### 6.3.1. Composition of the Medical Device

The investigational device 'Niti-S SPAXUS™ Stent' is used for drainage of cystic fluid by being connected to the pancreatic pseudocyst through human organs such as stomach or duodenum. It is composed with a stent made of nitinol and introducer system. The stent has a self-expandable structure in which the shape memory alloy wires made of nitinol are woven into a cylindrical mesh. The stent is designed to confirm the position of the stent as coated with a silicone membrane on the surface and insertion of a platinum marker.

The introducer system consists of two shafts. The proximal portion of the inner shaft is made of stainless steel and the distal and outer sheaths are made of thermoplastic material. The median inner diameter of the inner shaft is connected to the distal tip, and a guidewire (Optimos™ Guidewire, TaeWoong Medical Co., Ltd.) is placed through the median inner diameter to pass through the inner lumen. In addition, a blue zone is added to the outer sheath of this product to allow identifying the movement during the stent deployment on the endoscope. A tungsten x-ray marker is inserted into the 1st inner sheath which enables the expansion of the stent can be confirmed through the fluoroscope. The stent was also made of nitinol wires and a platinum marker is inserted to confirm the position of the inserted stent.

[figure not shown]
The following describes the dimensions and names of the Niti-S SPAXUSTM Stent and Introducer system model name.

<Figure 1. Dimensions of the Niti-S SPAXUSTM Stent & Introducer system by Model Name >

Art. No.	Body		Flare	
	Diameter (mm)	Length (mm)	Diameter (mm)	Length (mm)
SS0802FW	8	20	23	6.5
SS1002FW	10	20	25	6.5
SS1602FW	16	20	31	6.5

[figure not shown]
※ Allowable Error: Stent  $\pm 5\%$

[figure not shown]
Art. No.	Outer Diameter (mm)	Usable Length (cm)	Total Length (cm)
SS0802FW	3.3 (10Fr)	180	204
SS1002FW			204
SS1602FW			206

※ Allowable Error: Introducer system  $\pm 10\%$

<Figure 2. Part names of the Niti-S SPAXUS™ Stent & Introducer system>

No.	Part Name	Function
1	Stent Body	Consisted of Nitinol wire
2	Cover membrane	Prevents leakage and facilitates removal with silicone coating
3	Platinum Marker	X-Ray marker that identifies the stent position
4	Connector tube	Prevents Nitinol wire loosening
5	Flare	Prevents stent migration

No.	Part Name	Function
1	Hub	Pass the guidewire through the inner diameter
2	Pusher	Irrigation through the side hole
3	Y-Connector	Deliver the supporting force to stent when pulling the outer sheath during deployment of the stent
4	Outer Sheath	Block the expansion of the stent
5	2 nd Inner Catheter	deliver the force of pusher to the stent
6	Yellow Marker of Inner Diameter	Identify the location under the endoscope
7	1 st Inner Catheter	Pass the guidewire through inner diameter
8	Center X-Ray Marker	Identify radiation-opaque locations
9	Tip	Reduce resistance when progressing along the guidewire
10	Stent	Restore the expansion of stenosis
11	Holder	Anchoring of stent
12	Hole	Hole for passing of the guide wire
13	Side Hole	irrigation
14	Blue zone	Confirmation of stent deployment
15	Distal X-Ray Marker	Identify radiation-opaque locations

### 6.3.2. Instruction for Use

Endoscopic Ultrasound should be performed to determine the extent and shape of the lesion prior to stent insertion.

#### 1) Determination of Stent Size

- ① The length and diameter of the stent should be determined by the investigator after endoscopy and / or fluoroscopy.
- ② The length and diameter of the stent should be selected so that the walls of the two penetrating organs are at the closest proximity to each other so that it can be prevented from migration.

[figure not shown]
#### 2) Preparation of Stent Deployment

- ① Under endoscopic ultrasound guidance, a transluminal puncture is performed using a conventional endoscopic instrument (e.g. a fine-needle aspiration needle) in accordance with the preference of the investigator who operates the intervention, avoiding the blood vessels crossing at the position closest to the target pseudocyst.
- ② Introduce the guidewire (Optimos™ Guidewire, TaeWoong Medical Co., Ltd.) through the lumen of the needle which is used for puncturing into the target pseudocyst sufficiently, and remove the needle while leaving the guidewire in the cyst.
- ③ After removal of the needle, insert an dilating device such as a cystotome (or needle knife) and/or a balloon catheter along the guidewire until it is progressed across the lesion.
- ④ After dilating, carefully remove the dilating device.
- ⑤ Remove the stylet from the distal end of the introducer system.
- ⑥ Ensure that the valve of Y-connector connecting the inner sheath and outer sheath is locked by rotation proximal valve end in a clockwise direction to prevent premature stent deployment.

[figure not shown]
#### 3) Stent insertion method

Caution: Twisting or turning the introducer system during deployment can affect misplacement and stent performance

[figure not shown]
- ① Place the introducer system under the guidance of fluoroscopy and / or endoscopic ultrasound. The internal X-ray marker ('A') must pass through the wall of the pancreas or gallbladder.

[figure not shown]
- ② If the introducer system is located at the correct position, confirm whether the valve of the Y-connector is loosened by turning it counter-clockwise.
- ③ To begin stent deployment, immobilize the hub in one hand and grasp the Y-connector with the other hand. Gently slide the Y-connector back along the pusher towards the hub
- ④ Under EUS and fluoroscopic guidance, the distal flare is deployed inside of the target site
  - ➔ Slowly pull back the Y connector when the outer X-ray ring overlaps with the x-ray marker on the inner sheath
  - ➔ Check the opening of the distal flare.

- ⑤ Pull back the entire delivery system till seeing the blue marker of outer sheath under endoscopic view

- ⑥ Deploy the proximal flare of the stent under endoscopic guidance while making sure that the stent connects both walls together.

**Caution:** Do not push forward or pull backward on the hub with the stent partially deployed. The hub must be securely immobilized. Inadvertent movement of the hub may cause misalignment of the stent and possible damage.

4) After insertion of the stent

- ① Use a fluoroscope and an endoscope to confirm the expansion of the stent.
- ② Carefully remove the introducer system, guidewire and endoscope from the patient. If excessive resistance is felt during removal, wait 3~5 minutes to allow further stent expansion. (Place the inner sheath back into the outer sheath as the original state prior to removal)
- ③ Depending on the judgment of the investigator, the balloon dilatation inside the stent can be performed.

5) Routine procedures after insertion of the stent

- ① Assess the good position of the stent and effective drainage. A Stent may require up to 1 to 3 days to expand fully.
- ② It is possible to prescribe appropriate medication for each patient in accordance with the experience and decision of the investigator.
- ③ After the stent is implanted, a soft diet should be given according to the investigator's decision.
- ④ Observe the patient for symptoms of any complications.

6) Instruction for removal of the Niti-S SPAXUS™ stent

Remove the stent with forceps or snare carefully and smoothly.

#### **6.3.3. Storage Method and Expiration Date**

1) Storage before use

Store at 10 to 40 °C avoiding direct sunlight

2) Storage after use

The introducer system and the removed stent should be classified as the in-hospital medical waste and disposed after use in accordance with relevant laws and regulations since they are disposable items.

3) Expiration date

The items are valid to use for 2 years from the date of manufacture.

#### **6.3.4. Purpose of Use of Investigational Medical Device**

This investigational device is intended for the drainage of pseudocyst by connection to the pancreatic pseudocyst through adjacent organs such as stomach or duodenum.

## **7. STUDY OBJECTIVE**

This study was planned to confirm the effectiveness and safety of 'Niti-S SPAXUS™ Stent', a lumen-apposing, fully covered, self-expandable metal stent, being used for EUS-guided transluminal drainage for the treatment of pancreatic pseudocyst.

The primary objective is to assess whether the size of the pancreatic pseudocyst is reduced by more than 50% after the intervention to confirm the clinical effectiveness of the Niti-S SPAXUS™ stent.

The secondary objective is to evaluate the incidence and mean of the followings to determine the effectiveness and safety of the Niti-S SPAXUS™ stent.

- Technical success
- Stent lumen patency
- Stent removal success
- Procedure time
- Procedure / Device related serious adverse events
- Other adverse events

## 8. EXPECTED STUDY PERIOD

It is expected that the study implementation will take about 15 months after the approval of the clinical investigation plan obtained from the Ministry of Food and Drug Safety and the IRB, including 12 months for the subject enrollment period and 3 months for the follow-up period at maximum. Afterwards, it will take about 3 months for data processing, statistical analysis and preparation of the clinical study report additionally.

- Subject recruitment: 12 months
- Follow-up observation period: 3 months
- Data processing and statistical analysis: 2 months
- Preparation of the clinical study report: 1 month

## 9. SUBJECT SELECTION AND SAMPLE SIZE

### 9.1. Subject Selection

#### 9.1.1. Inclusion Criteria

Patients who meet all of the following inclusion criteria may be enrolled in this study.

- ① Male and female adults over 19 years of age
- ② Patients diagnosed with pancreatic pseudocyst who satisfy the following criteria and who

require the drainage treatment.

- When the size of the pseudocyst is 6 cm and larger (based on the maximum cross-sectional area on CT)
- When the fluid content of the pseudocyst is more than 70%
- When the pseudocyst is in a position to allow transluminal drainage

③ When the patient is willing to participate in the clinical study complying with treatments and procedures, and to visit the hospital for all follow-up evaluations.

④ When the patient heard a description of the purpose, method and effectiveness of this clinical study and has voluntarily signed a written informed.

#### 9.1.2. Exclusion Criteria

Patients who meet any item of the following exclusion criteria will not be enrolled in this study.

- ① When the patient cannot use appropriate contraception as a woman of childbearing age, or when the patient is pregnant or breastfeeding
- ② When the patient is not possible to undergo the endoscopic intervention
- ③ When an effective drainage is difficult due to severe septation in pseudocysts
- ④ When the patient is severely allergic to contrast agent and Nitinol, etc
- ⑤ When the patient has a hemorrhagic disease or coagulation disorder (e.g. DIC)
- ⑥ When the platelet count is less than 60,000 cells/mm^3 or exceeds the International Normalized Ratio (INR) 1.5
- ⑦ When the patient has hemodynamic instability (e.g. shock)
- ⑧ When the patient has immunosuppressive diseases such as malignant tumors and bone marrow transplantation, or is receiving immunosuppressive treatments such as chemotherapy or immunosuppressive drugs
- ⑨ If the patient has any active infectious disease requiring antibiotic treatment, such as known or suspected meningitis or endocarditis
- ⑩ If the patient has any psychiatric illness or conditions that makes participation in the clinical study impossible (e.g. dementia, seizure)
- ⑪ If the patient has participated in other clinical studies for medicines or medical devices within the last 3 months
- ⑫ When the investigator determines that the Niti-S SPAXUSTM Stent procedure is not possible for the patient

## 10. STUDY METHOD AND PROCEDURE

### 10.1. Study Design

The study is designed to be conducted as a prospective, multi-center, single arm, non-inferiority, open-label study to confirm the effectiveness and safety of the Niti-S SPAXUS™ Stent, being used for EUS-guided transluminal drainage in patients with pancreatic pseudocyst. It will be performed in a total of 35 patients at 6 institutions.

## 10.2. Observation Items · Clinical Lab Test Items and Observational Test Method

### 10.2.1. Laboratory tests

The laboratory tests will be carried out at every visit from the baseline (within 7 days of the procedure), and the following items will be included.

- Hematological test : CBC, WBC differential count
- Blood Coagulation Test : PT, aPTT, INR
- Serum chemistry test : Total bilirubin, Direct bilirubin, AST, ALT, Alkaline Phosphatase,  $\gamma$ -GT, glucose, Amylase, Lipase, CRP
- Pregnancy Test : The pregnancy will be tested at the baseline (within 48 hours of the procedure) in women of childbearing ages, using a urine test (or  $\beta$ -HCG) for confirmation

### 10.2.2. Clinical symptoms

The clinical symptoms will be checked at every visit from the baseline and the following items will be included as the pancreatic pseudocyst-related symptoms.

- Abdominal Pain
- Nausea
- Vomiting
- Anorexia
- Diarrhea
- Others (e.g. fever, a tender mass in abdomen)

### 10.2.3. Radiological Examination (X-ray)

X-ray (abdomen) will be performed at baseline, on the day of procedure (Day 1), on the following day of procedure (Day 2), at Discharge (Day 5  $\pm$  2 days), and at Day 20 after stent removal, and the following items will be evaluated by the investigator.

- Location and status of the stent
- Presence/absence of the stent fracture
- Presence/absence of the stent migration

### 10.2.4. Abdominal CT Scanning

The abdominal CT scanning will be conducted on the baseline and at the time point of the stent removal (Day 30 and/or 60), and the following items will be evaluated by the investigator.

- Size of the pancreatic pseudocyst
- The extent of Fluid content contained in the pancreatic pseudocyst

### **10.2.5. Endoscopy**

This will be performed at the time point of the stent removal (Day 30 and/or 60) and the stent lumen patency will be evaluated by the investigator.

## **10.3. Study Methods**

### **10.3.1. Screening /Baseline**

<Visit 1>

Among patients diagnosed with pancreatic pseudocysts via abdominal ultrasonography, endoscopic ultrasound, abdominal computed tomography (CT), or magnetic resonance imaging (MRI), those who are required to undergo the EUS-guided transluminal drainage will be referred to this clinical study. After the patient heard a description of the purpose, method and effectiveness of this clinical study and has voluntarily signed a written informed consent, when the patient satisfies the inclusion • exclusion criteria, will be enrolled to this clinical study from implementation of the following procedures as specified in the clinical study schedule, and will be assigned with the subject identification code.

The following procedure will be performed during screening / baseline visit.

- Demographics and Physical Measurement (Date of birth, Gender, Alcohol drinking, History of smoking, Height and Weight)
- Vital Signs (Blood pressure, Pulse rate, Respiration rate, Body temperature)
- Physical Examination
- Medical History / Allergy (Significant past medical and surgical History, Current medical history, Medications and Other allergies)
- Laboratory tests (Hematology, Coagulation, Chemistry, and Pregnancy Test for women at childbearing age)
- Clinical symptoms
- Radiological Examination (X-ray: abdomen)
- CT Scanning (abdominal CT)
- Concomitant Medications /Procedures

### **10.3.2. Day of Procedure**

< Visit 2>

Subjects who meet all criteria for the inclusion • exclusion will be admitted to the hospital on the day before the procedure in accordance with the clinical standard of the institution and will undergo the EUS -guided transluminal drainage using the SPAXUS stent. The following procedure shall be

performed on the day of the procedure and the subject should stay in the hospital for at least one day or more after the procedure for observation of the progress.

- Vital Signs (Blood pressure, Pulse rate, Respiration rate, Body temperature)
- EUS-guided transluminal drainage with Niti-S SPAXUS™ Stent
- Laboratory tests (Hematology, Coagulation, Chemistry)
- Clinical symptoms
- Radiological Examination (X-ray: abdomen)
- Concomitant Medications /Procedures
- Adverse Events /Serious Adverse Events

#### **10.3.3. Follow-Up Observation**

< Visit 3>

After the procedure of the Niti-S SPAXUS™ Stent, the subjects will be observed for the post-procedure treatment and progress in accordance with the clinical standard of the institution. On the following day of the procedure (Day 2), the investigator will confirm the location and deployment state of the stent and the stent lumen patency through clinical symptoms, laboratory tests and radiological examination, and evaluates the clinical symptoms and the adverse events. Then, the following procedures will be performed.

- Vital Signs (Blood pressure, Pulse rate, Respiration rate, Body temperature)
- Physical Examination
- Laboratory tests (Hematology, Coagulation, Chemistry)
- Clinical symptoms
- Radiological Examination (X-ray: abdomen)
- Concomitant Medications /Procedures
- Adverse Events /Serious Adverse Events

< Visit 4>

Subjects enrolled in this study will have a follow-up visit at the time of discharge (Day 5 ± 2 days) and the following procedures will be performed at the visit.

- Vital Signs (Blood pressure, Pulse rate, Respiration rate, Body temperature)
- Physical Examination
- Laboratory tests (Hematology, Coagulation, Chemistry)
- Clinical symptoms
- Radiological Examination (X-ray: abdomen)
- Concomitant Medications /Procedures
- Adverse Events /Serious Adverse Events

< Visit 5>

At Day 30 ( $\pm$  10 days) after the procedure, abdominal CT scanning will be performed to confirm the resolution of the pancreatic pseudocyst which is the primary effectiveness endpoint of the study, and to assess the clinical success. If the subject meets the criteria for stent removal through such as laboratory tests, clinical symptoms and abdominal CT scanning by the judgement of the investigator, the stent will be removed using an endoscope and the following procedures will be performed.

- Vital Signs (Blood pressure, Pulse rate, Respiration rate, Body temperature)
- Physical Examination
- Laboratory tests (Hematology, Coagulation, Chemistry)
- Clinical symptoms
- CT Scanning (abdominal CT)
- Removal of Niti-S SPAXUSTM Stent (using endoscopy)
- Evaluation of clinical success
- Evaluation of the stent removal success
- Concomitant Medications /Procedures
- Adverse Events /Serious Adverse Events

< Visit 5-1>

If the subject fails to meet the criteria for stent removal at Day 30 after the procedure, the procedure the investigator will evaluate whether the stent is removable through the laboratory tests, clinical symptoms, and abdominal CT scanning at Day 60 ( $\pm$  10 days) after the procedure. If the drainage is not achieved sufficiently at Day 60 after the procedure and the placement of the drainage tube is required (e.g. untreated pancreatic pseudocysts communicated with the main pancreatic duct), the Niti-S SPAXUSTM stent will be removed and a plastic stent will be inserted. The following procedures will be performed.

- Vital Signs (Blood pressure, Pulse rate, Respiration rate, Body temperature)
- Physical Examination
- Laboratory tests (Hematology, Coagulation, Chemistry)
- Clinical symptoms
- CT Scanning (abdominal CT)
- Removal of Niti-S SPAXUSTM Stent (using endoscopy)
- Evaluation of clinical success
- Evaluation of the stent removal success
- Concomitant Medications /Procedures
- Adverse Events /Serious Adverse Events

< Visit 6>

At Day 20 ( $\pm$  10 days) after removal of the stent, an evaluation of the investigational device and the procedure-related adverse events will be performed and the following procedures will be performed.

- Vital Signs (Blood pressure, Pulse rate, Respiration rate, Body temperature)
- Physical Examination
- Laboratory tests (Hematology, Coagulation, Chemistry)
- Clinical symptoms
- Radiological Examination (X-ray: abdomen)
- Concomitant Medications /Procedures
- Adverse Events /Serious Adverse Events

#### **10.3.4. Concomitant Therapies**

All medical devices (e.g. plastic stent) and medications that may affect the effectiveness or safety of the investigational device are prohibited. Prophylactic antibiotics will be administered according to the clinical standard of the institution, and the post-procedure administration of all conventional drugs such as analgesics and digestive agents is allowed. All drugs taken prior to the enrollment in the clinical study due to underlying diseases and any additional drugs added after the Niti-S SPAXUSTM stent implantation should be recorded in the case report form.

#### **10.4. Subject Identification Code**

The patients determined as confirming to the inclusion • exclusion criteria after giving the written informed consent to participate in the clinical study, will be enrolled in this study. The subjects enrolled in the study will be assigned with the subject identification code sequentially, and they will be given a total of four digits including the 2 digits of the institution number in order of 01, 02, 03 and etc.

e.g. 

0	1	-	0	2
---	---	---	---	---

 The subject's identification code of the 2nd enrollment subject from the first institution.

### **11. STUDY EVALUATION**

The primary and secondary effectiveness assessments will be conducted by the investigator based on the results of clinical symptoms, laboratory tests, endoscopy, X-ray and abdominal CT scanning.

## 11.1. Effectiveness Assessment

### 11.1.1. Effectiveness Endpoints

- 1) Primary Effectiveness Endpoints
  - Clinical success
- 2) Secondary Effectiveness Endpoints
  - Technical success
  - Stent lumen patency
  - Stent removal success
  - Procedure time

### 11.1.2. Effectiveness Assessment Criteria and Methods

- 1) Primary Effectiveness Assessment

- Clinical success

When the size of pancreatic pseudocyst confirmed by abdominal CT at Day 30 or 60 ( $\pm$  10 days) after the procedure of the Niti-S SPAXUSTM stent is reduced by 50% at least compared with the baseline, it will be evaluated as clinically successful.

- 2) Secondary Effectiveness Assessment

- Technical success

If the stent is deployed successfully in the gastrointestinal tract and the pseudocyst, and if the drainage is confirmed visually, it is considered technically successful.

- Stent lumen patency

The stent lumen patency will be evaluated by the investigator at Day 30 or 60 ( $\pm$  10 days) after the procedure of the Niti-S SPAXUSTM stent through clinical symptoms and endoscopy.

- Stent removal success

When the Niti-S SPAXUSTM Stent is successfully removed by using forceps or snare through endoscopy as the treatment is succeeded clinically at Day 30 or 60 ( $\pm$  10 days) according to standard procedures and the criteria for stent removal are met, it is considered as the stent removal success. At Day 30 after the procedure, if the investigator determines that the removal criteria are not met and that a further stent drainage is necessary, the possibility of stent removal at Day 60 ( $\pm$  10 days) after the procedure is evaluated again and the Niti-S

SPAXUS™ Stent will be removed at the time point. However, if sufficient drainage is not achieved even at the maximum of 60 days and a drainage tube (e.g. an untreated pancreatic pseudocyst communicated with the main pancreatic duct) is needed, the Niti-S SPAXUS™ stent will be removed and a plastic stent will be inserted. Plastic stent insertion is not applicable to a clinical success.

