#### Criteria for Stent Removal

The size of the pancreatic pseudocyst is reduced to 3 cm or less based on the maximum cross-sectional area on the CT or the time point of 60 days after stenting

- Procedure time

The time is measured from the moment that the endoscope is inserted into the oral cavity to the time point at which the endoscope is removed.

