### **12.6. Expected Adverse Events and Precautions for Use**

#### **12.6.1. Expected Adverse Events**

< Expected Adverse Events during the procedures of the Niti-S SPAXUSTM Stent >

- Bleeding
- Stent misplacement
- Inadequate expansion
- Stent migration
- Pain
- Perforation

< Expected Adverse Events after Deployment of the Niti-S SPAXUSTM Stent >

- Bleeding
- Pain
- Perforation
- Stent misplacement
- Stent migration

- Stent occlusion
- Fever
- Pancreatitis
- Abscess formation
- Vomiting
- Pneumoperitoneum
- Intraperitoneal leakage
- Peritonitis
- Hematoma
- Inflammation
- Infection
- Fistula
- Ulceration
- Sepsis
- Rupture of intracystic artery
- Stent removal failure

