#### 14.2.2.2. Analysis of Secondary Effectiveness Assessment

Regarding the secondary effectiveness variables, for categorical data, the frequency and percentage as well as 95% confidence interval will be presented. For continuous data, descriptive statistics (number of cases, mean, standard deviation, median value, maximum and minimum values) are provided

- Technical success
- Stent lumen patency
- Stent removal success
- Procedure time

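### Stent removal success also requires clinical success, so its rate is capped by the clinical success rate and does not measure removability on its own

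*Combined protocol and SAP*

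**What the plan says.** Section 11.1.2 defines stent removal success by three joined elements. The stent "is successfully removed by using forceps or snare through endoscopy as the treatment is succeeded clinically at Day 30 or 60", "and the criteria for stent removal are met, it is considered as the stent removal success". The middle element is the primary endpoint: the same section calls a subject a clinical success when the pseudocyst size on CT "is reduced by 50% at least compared with the baseline, it will be evaluated as clinically successful".

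The removal criteria, set out at the end of 11.1.2, can be met in two ways: the pseudocyst has shrunk to 3 cm or less "on the CT or the time point of 60 days after stenting". The second route depends on time alone.

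The plan expects stents to be removed in subjects who have not succeeded clinically. Note 11 to the Clinical Study Schedule, the Visit 5-1 text in 10.3.3, and 11.1.2 itself all cover this case. In the last, where drainage is still inadequate at Day 60, the "stent will be removed and a plastic stent will be inserted. Plastic stent insertion is not applicable to a clinical success".

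For analysis, 14.1 and 14.1.1 make the FAS the main set for effectiveness: subjects who had the procedure and have a primary assessment. Section 14.2.2.2 says of the secondary endpoints that "for categorical data, the frequency and percentage as well as 95% confidence interval will be presented". No separate denominator is given for removal success. Section 12.6.1 lists "Stent removal failure" as an expected adverse event.

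**The concern.** An endpoint with this name should answer a device question: once placed, can the stent be taken out endoscopically with forceps or snare? As defined, it answers a joint question: did the stent come out, and did the cyst also shrink enough?

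The subjects affected are those whose stent is removed at Day 60 after inadequate drainage. They are in the FAS if they have the CT assessment, and they meet the removal criteria on time. The clinical-success clause alone stops a clean removal from counting. The percentage in the effectiveness table would then move with the primary endpoint even when removability is constant. A reader of that single figure could take a shortfall in clinical success for difficulty in removing the device. The effectiveness table could also appear to disagree with the adverse event table, which would show no removal failure for the same subjects.

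**Working it through.** **Inputs.** Expected clinical success 96%, 31 evaluable and 35 recruited subjects, and 86.2% clinical success for a marketed lumen-apposing stent (all 9.2); 71% as the low end of the range in existing studies (9.2, margin rationale). The plan gives no expected value for removal success and no method for its confidence interval. Two assumptions are therefore needed: every stent is removed cleanly, and intervals are exact (Clopper-Pearson).

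**The plan's own figure.** n = (1.960 + 0.842)² × 0.96 × 0.04 / (0 − 0.10)² = 30.14, rounded up to 31; 31 / 0.90 = 34.4, rounded up to 35. Both stated figures reproduce. They concern the primary endpoint and do not depend on this point.

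**How the definition applies to each kind of subject.**

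| Subject | Removal criteria | Clinical success | Clean endoscopic removal | Removal success as written |
|---|---|---|---|---|
| Cyst 3 cm or less and at least halved, stent out at Day 30 | met on size | yes | yes | yes |
| Cyst at least halved but above 3 cm, stent out at Day 60 | met on time | yes | yes | yes |
| Cyst not halved, or plastic stent needed, stent out at Day 60 | met on time | no | yes | **no** |
| Clinical success, stent cannot be removed with forceps or snare | met | yes | no | no |

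The third and fourth rows receive the same result for different reasons.

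**Size.** As written, the rate is P(clean removal and clinical success), which cannot exceed P(clinical success). With P(clean removal) = 1 and a FAS of 31:

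| Clinical success | Expected count | Reported as written (95% CI) | Clean removals not counted |
|---|---|---|---|
| 96% | 31 × 0.96 = 29.8, about 30 | 30/31 = 96.8% (83.3% to 99.9%) | 1 |
| 86.2% | 31 × 0.862 = 26.7, about 27 | 27/31 = 87.1% (70.2% to 96.4%) | 4 |
| 71% | 31 × 0.71 = 22.0, about 22 | 22/31 = 71.0% (52.0% to 85.8%) | 9 |

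With removal alone as the endpoint, all three rows would read 31/31 = 100% (88.8% to 100%).

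**Sensitivity to the clean-removal assumption.** If 95% of stents come out cleanly, independently of clinical success, the endpoint reads 0.95 × 0.96 = 91.2%, 0.95 × 0.862 = 81.9% and 0.95 × 0.71 = 67.5%. Removability is 95% in each case.

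**The case against.** The strongest objection is about wording. The English is awkward, and the clause on clinical success may only describe the usual setting for removal. The time-only route in "or the time point of 60 days after stenting" sits badly with a strict clinical-success condition, which favours that reading. It is possible. However, no other section defines the endpoint as removal alone, and the same paragraph goes on to say that inserting a plastic stent is not a clinical success. Section 10.3.3 asks for removal success to be evaluated at Visit 5-1, when stents still in place, including those in unresolved cysts, come out. Six sites would have to classify those subjects from this sentence, and its literal sense points to not a success.

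Three stronger conclusions are tempting, and the documents do not support them:

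- *The endpoint merely repeats the primary.* It does not. A clinical success whose stent cannot be removed endoscopically is a primary success and a removal failure, so clean removal is still one component.
- *The trial cannot tell a retained stent from a cyst that did not shrink.* That is true of the single percentage only. Sections 12.5.1, 12.6.1 and 14.2.3 record and tabulate removal failure as an adverse event, and 10.3.3 evaluates clinical success and removal success as separate items.
- *The longest-dwelling or hardest removals are left out.* Taking size as a diameter, a cyst that goes from 10 cm to 4 cm has shrunk by 60%. It is a clinical success above the 3 cm criterion, so its stent can stay until Day 60 and still count. Nothing in the plan says that removal is harder in clinical failures.

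A denominator restricted to clinical successes would remove the cap, but the rate would then describe that subgroup only, and the plan states the FAS. It is also fair to say that the endpoint is one of four secondary endpoints, carries no hypothesis test, and errs against the device.

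**Conclusion.** The definition is wrong as written. Followed literally in the FAS, it scores clean endoscopic removals in clinical failures as not successful, so the reported rate is capped by the clinical success rate and is not a measure of removability on its own. The understatement is about one subject in 31 if clinical success is near the assumed 96%, and about four in 31 at 86.2%, on the assumption that every stent comes out cleanly.

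The reach is limited. The result is secondary and descriptive. The primary analysis, sample size and power do not change, and a true removal failure would still be visible in the safety data. The conclusion rests on the literal reading of 11.1.2 and on the FAS as denominator, because nothing else is stated.

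**What to change.** In 11.1.2, define stent removal success as endoscopic removal of the study stent with forceps or snare, whatever the clinical outcome. Take two conditions out of the endpoint definition: the clinical-success clause that ends "is successfully removed by using forceps or snare through endoscopy as the treatment is succeeded clinically at Day 30 or 60" and the removal-criteria clause that opens "and the criteria for stent removal are met, it is considered as the stent removal success". Taking out only the first would still leave the endpoint dependent on cyst size for any removal before Day 60. The rules on when the stent is removed stay as they are; only what counts as the endpoint changes.

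In 14.2.2.2, state the denominator: all subjects with a placed stent in whom removal was attempted. Add a matching exception to the FAS rule in 14.1.1 and to the missing-data statement in 14.2.4, since both tie effectiveness results to subjects with the primary assessment. Removal can still be tabulated by clinical success for readers who want the joint result.

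The cost is a few sentences in four places. Removal success is already evaluated at Visits 5 and 5-1, so no visit, test or data item is added. The one small drawback is that this endpoint's denominator will differ from the FAS used for the other effectiveness results, and the table should say so.
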